1 R61 AT010712-01

Tool Revision History

Version Number: 2.0b

Version Date: November 4, 2019

Summary of Revisions Made:

Page 11 (Bayley's III assessment) - Apologies. The statement about Bayley's III developmental assessment was not supposed to be included in R61 study protocol. It is part of the R33 protocol. I am deleting it from this section.

Page 14 (how will they maintain distance of headphones relative to baby's ears) - In this age group, these preterms have very little motor capability to move much – even while awake. In addition, during each session of intervention, study staff will be monitoring for infant discomfort. Study staff will also monitor to ensure the 1cm distance from the preterms' ears.

Page 15 (hearing loss) - Hearing testing is not typically assessed in preterm babies, but rather at term age. However, hearing loss in preterm babies typically occurs in those who are medically unstable (hyperbilirubinemia, sepsis, or meningitis – approximately 2-4% of the population). That population of preterm infants do not meet eligibility criteria for this trial. Hearing will also be confirmed during ERP testing.

Page 22 (blinded statistician) - Yes. This statistician is only aware of the blinded treatment and is thus blinded also for the study analysis.

Page 27 & 28 (why is PIPP considered the primary outcome but not associated with primary study objective 1) - This R61 is exploratory with little prior research in all aspects, and thus we had challenges regarding sample size/ power considerations. Our main goal is aimed towards meeting Go/NoGo Criteria – each with equal weight in mind. Certainly, the order in which all the Go/NoGo criteria is presented can be switched around with primary outcome PIPP being Primary objective. With minimal prior research, we decided on PIPP to be the primary outcome for statistical calculations. In this exploratory work there is not adequate power to assess hypothesis 1 and 2.

I have put together a version 2.0b study protocol response to these edits with the objectives moved around. Version 2b shows PIPP primary outcome to be associated with primary objective.

Page 28 (eligibility) - Yes. The eligible subjects at the University of Minnesota Neonatal Intensive Care Unit meeting inclusion and exclusion criteria.

Page 29 (missing data) - please see added section 9.6 Missing Data.

Page 29-30 (clarification about sleep duration measure) - Milestone threshold is reached if any 1 or more of the serial EEGs is reached. This threshold was purposely chosen as brain maturation occurs at different stages. This exploratory investigation is important to understand whether there might be critical time periods during prematurity in which the music intervention may have more impact. If the other time points show opposite directions, these may be time periods in which music may be less effective. Because no literature is available to describe this, it is important for us to gather this information. Page 30-31 (clarification about PIPP/central EEG amplitudes) – similar answers to the above sleep measure regarding importance of reaching thresholds at different time points of prematurity.

Version Number: 2.0c

Version Date: February 7, 2020

Updated inclusion criteria to 30 weeks +/- 2 weeks

Version Number: 3.0

Version Date: June 18, 2020

Page 13: PIPP performed during heel lance procedure expanded to include both Minnesota Newborn Screen or required heel lance blood tests

The PIPP is performed when the preterm infant undergoes the heel lance procedure for either the Minnesota Newborn Screen or other required blood tests performed during the same approximate time period within the scheduled protocol timeline. The PIPP should not pose any additional risk to the subject as the heel lance for newborn screening or required blood tests are both standard of care.

The heel lance procedure for the Minnesota Newborn Screen is the same as the heel lance procedure required for other blood tests. Due to new COVID restrictions and limited access to the NICU for research purposes, the opportunity to perform the PIPP has been expanded to include other required blood tests that utilize the same heel lance procedure performed at approximately the same time period within the scheduled protocol timeline. These heel lances are all part of required standard of care and does not significantly change the study protocol.

Page 15 Diagram:

Changed label to Standard Heel Lance Procedure

Confirm eligibility, obtain consent, enroll Standard Heel Lance Procedure

Preterms born at 30 weeks (+/- 2 weeks)

Instead of Newborn Screen Heel Lance

Page 19: Visit 5/Completion Visit:

- 1) Added Medical History Review to gather information if there are any ongoing medical issues that might affect ERP results
- 2) Added music exposure form to gather information on how much music is played at home after NICU discharge

Version Number 4.0

Version Date: August 31, 2020

Page 5, 15, 17, 18, 25: COVID efforts:

Given the need to decrease face to face interactions for COVID precautions, we are slightly decreasing the number of music intervention to an average of 4-5 (instead of 5-6) sessions per week. This is still

frequent enough music intervention to show changes in pain responses and neurodevelopmental findings since the intervention lasts a target of 6 weeks.

Page 5: ...average 4-5 intervention or control sessions per week...

Page 15: MBI subjects will receive ... intervention averaged at 4-5 sessions per week.

Page 17: ...music intervention 4-5 sessions per week...

Page 18: Adherence ...as 80% compliance ...average of 4-5 intervention or control sessions per week Page 25: Targeted averaged 4-5 sessions of MBI or Control will be played per week.

Page 16 and 18: Change 6 to 10 playlists:

To randomize songs properly, our biostatistician created 10 playlists, instead of the 6 originally planned. Page 16: stimulation, habituation, and neurological development, we will use ten playlists. Page 18: As it is recommended to change song order to increase stimulation, habituation, and neurological development, we will use 10 playlists.

Page 16: "decibel" to "volume":

The mp3 player/headphone equipment decibel levels will be checked prior to use. Because the mp3 players only display volume levels, this word was changed from "decibel" to "volume".

Page 16: Daily electronic volume level checks will avoid the need for listening checks of the headphones.

Version Number 5.0

Version Date: March 16, 2021

Pg 14: Clarification that for reliability in scoring, the PIPP will be

done by 2 study team members. The 2nd PIPP can be done in-person or virtually.

Pg 21 and 23 (sec 6.1 and 6.2.2 clarification that HADS is optional for the parent to complete)

Pg 24 (sec 6.2.4): clarification that EEG will have a video component

Pg 25: Hearing status of the child will be confirmed through chart review of the child's clinical BAER hearing test. This is done clinically prior to discharge (and/or at 1 month clinical care follow-up).

Pg 36 (sec 11.3) clarification the confidentiality of the video EEG

Version Number 6.0

Version Date: August 11, 2021

Updated protocol to reflect that ERPs will be conducted between 43-48 weeks corrected gestational age. See pgs 10,11,15,16, 26, 30. No impact on analysis. This allows for better compliance with allowing for scheduling families with a new born child.

Version Number 7.0

Version Date: February 1, 2022

Pg 20: Updated Section 6.1 Schedule of Evaluations – Screening and Study Visits to remove the 48 hour time period for baseline/visit 1 activities to occur. This change is administrative only as it has no impact on study aims, analysis or safety.

Version Number 8.0

Version Date: March 8, 2022

Pg 20-21: *Updated Section 6.1 Schedule of Evaluations &* Pg 25: *Section 6.2.4 Follow up Visits: Visits 2-5* to move Family Feedback form completion at Visit 4, noting though that this may be completed at any time prior to discharge.

TABLE OF CONTENTS

Page
FULL PROTOCOL TITLE
1 R61 A1010/12-01 1
Tool Revision History
TABLE OF CONTENTS 7
STUDY TEAM ROSTER
PARTICIPATING STUDY SITES
PRÉCIS 13
1. STUDY OBJECTIVES 14
1.1 Primary Objective (1) 14
1.2 Primary Objective (2) 15

6) Study Coordinators (TBD) – Study coordinators will oversee practical details of the project, including coordinating recruitment, implementation of intervention, organizing details of data collection, data movement, data storage, data security, and data access; data preparation for publications and project reporting.

Contact info TBD

PARTICIPATING STUDY SITES

[name]

University of Minnesota (Department of Neurology)

[name] Office: [contact] [contact] email: [contact]

PRÉCIS

Study Title

Effects of Music Based Intervention (MBI) on Pain Response and Neurodevelopment in Preterm Infants

Objectives

Primary Objective (1):

Characterize differences in preterm pain responses between MBI and controls

Primary Objective (2):

Identify differences between MBI and controls in preterm brain maturation and early neurodevelopment

Design and Outcomes

Study design: Pilot prospective randomized, double blinded, controlled study to test effect of music based intervention (MBI) on pain response and neurodevelopment in preterm infants.

Aim 1 (R61): Characterize differences in preterm pain responses between MBI and controls.

The objective of this aim is to understand the behavioral processes of MBI on pain in preterm infants by comparing the PIPP and EEG pain responses in the MBI and control cohorts.

Aim 2 (R61): Identify differences between MBI and controls in preterm brain maturation and early neurodevelopment.

The objective of this aim is to explore biological mechanisms of MBI on preterm brain maturation and neurodevelopment using electroencephalography (EEG) and event related potentials (ERPs).

Interventions and Duration

Specific recorded lullables will be played for 6 weeks (+/- 1 week). Additional follow-up will occur at 43-48 weeks corrected age (~ one month old after the original due date).

Sample Size and Population

Recruit 60 medically stable preterm infants born at approximately 30 weeks to participate in this study. Randomization will be stratified by sex at birth and within each stratum use randomly allocated block sizes of 2 and 4.

1. STUDY OBJECTIVES

1.1 **Primary Objective (1)**

Aim 1(R61): Characterize differences in preterm pain responses between MBI and controls.

Premature infant pain profiles (PIPP) include physiologic, behavioral, and contextual measures which identifies differences in pain responses between MBI and controls while still in the neonatal intensive care unit (NICU). Central EEG amplitude changes have been time-locked with painful procedures in term infants. We will explore if PIPP scores and central EEG amplitude changes are attenuated with MBI in comparison to controls.

• Hypothesis 1: MBI will show improved pain responses, with lower PIPP

scores and attenuated central EEG amplitude changes during painful procedures, in comparison to the control cohort.

1.2 Primary Objective (2)

Aim 2(R61): Identify differences between MBI and controls in preterm brain maturation and early neurodevelopment.

EEG is a surrogate marker for real time brain function during sleep-wake cycles. Because preterm brain networks develop during sleep, sleep duration is a strong indicator of brain maturation. Serial biweekly EEGs of preterm infants can quantify sleep duration trends and track MBI's influence on sleep. To enhance objectivity, innovative EEG machine-learning tools will be applied to the analyses.

• Hypothesis 2: MBI will enhance preterm EEG brain maturation in comparison to controls.

Due to the natural limitations of evaluating immature neonatal nervous systems, ERPs have been utilized to study early neurodevelopment. ERPs quantify electrical brain potentials changes time-locked with a stimulus. Auditory ERPs performed at 1 month (43-48 weeks) corrected age evaluates attention and discrimination between familiar and novel stimuli - early neurodevelopmental signs of recognition memory function and perceptual learning.

• Hypothesis 3: ERPs at 1 month (43-48 weeks) corrected age will show that MBI has a greater impact on early neurodevelopment when compared to controls.

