Nevertheless, music has the remarkable ability to enhance child neurodevelopment. Auditory listening has been found in 27 week fetuses.¹⁰ Fetal auditory learning discriminates low-pitch sound features such as rhythm of music and prosodic features of speech¹¹ and fetuses perceive high-pitched sounds in a similar manner that adults recognize speech sounds.¹² Infants exposed to music prenatally have been shown to recognize familiar melodies at 4 months old suggesting that early music exposure can form lasting neural representations in the brain.¹³ Preterm music listening has been found to increase immediate sleep duration, enhance physiologic functioning (heart rate and oxygen saturation levels), improve behavioural states and weight gain while decreasing hospital stays and initial weight loss.^{14,15} Early music training is associated with enhanced neural speech processing such as pitch changes in speech sounds¹⁶ syllable duration¹⁷ and improved verbal memory skills.¹⁸ Music-based interventions (MBIs) for infants are low-risk¹⁹, minimallyinvasive, and low-cost,²⁰ and thus, an ideal intervention to trial in the neonatal intensive care unit (NICU). The NICU is a necessary but artificial environment created for the survival of preterm infants. It is imperative to carefully select their exposures in this unique environment which overlaps with the timing of the third trimester of pregnancy, a sensitive growth period in which we can have a great impact on immediate and future neurodevelopment.

2.2a Study Rationale – Primary Objective (2)

Thus, we propose a novel approach to study the effects of a longer duration of repeated MBI (6 weeks) by utilizing objective and reproducible measures of electroencephalography (EEG) and event related potentials (ERPs). EEG captures electrical potential oscillations of the brain which yields valuable

information about brain function.²⁵ EEG trends over time reveal brain maturation in preterm infants. Utilizing EEG is a novel approach to studying the biological mechanisms of MBI effects on preterm infants as EEG is objective, captures real-time brain activity, and tracks overall changes in neurodevelopment (Aim 2). Furthermore, ERPs test recognition memory function and cognitive processing of mother vs stranger's voice and offers another objective measure to further study the early effects of the MBI's biological mechanisms on neurodevelopment of these infants (Aim 2).

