9.5 Outcomes: Milestone Measures and Data Analyses

Measure 1: Average sleep (REM+nonREM) duration difference between MBI and controls using EEG. Normal preterm brain development is dependent on cycling between wakefulness and sleep with sleep durations gradually increasing by about 5% increments every two weeks until term age. EEG will be used to measure the average duration of sleep (REM + non-REM) between MBI and controls. Average sleep duration measurements will determine if MBI promotes/enhances brain maturation.

Statistical Analysis: Four quality sleep durations from within each EEG session will be averaged per-infant per-timepoint (one EEG session for each of the 4 age timepoints, 30 weeks, 32 weeks, 34 weeks, 36 weeks). At each timepoint, average sleep duration will be compared between MBI infants and controls. Milestone threshold will be reached if >5% longer average durations of sleep are found in the MBI cohort compared to controls in any 1 or more of the serial EEGs.

Measure 2: Late Slow Wave amplitude difference in auditory ERPs comparing MBI to controls. Due to immature nervous systems, early infant neurodevelopment studies have centered on attentional capture paradigms using ERPs. ERPs quantify changes in electrical brain potentials time-locked to a stimulus and are widely used to study cognitive abilities such as learning, discrimination, attention, and memory. At one month age, the ERP Late Slow Wave of a mom/stranger stimulus is considered a reflection of perceptual learning and memory. ERP Late Slow amplitude measurements will determine if MBI enhances neurodevelopment.

Statistical Analysis: ERP Late Slow Wave amplitudes from the 100 trials of the auditory recognition task will be averaged. Within-infant average Late Slow Wave amplitudes across mother's voice trials minus the same average across stranger's voice trials will be computed and averaged. Mother-vs-stranger Late Slow Wave average difference between MBI and controls will be compared. Milestone threshold will be reached if $\ge 1 \ \mu V$ greater amplitude difference in ERPs of the MBI cohort compared to controls is found at one month adjusted age.

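### Measure 1 compares sleep duration visit by visit and never estimates its change with age, so a gap already present at the first EEG can be read as enhanced maturation

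*Combined protocol and SAP*

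**What the plan says.** Section 1.2 (Primary Objective 2) names sleep duration as the marker: "sleep duration is a strong indicator of brain maturation". It then gives the repeated recordings their purpose: "Serial biweekly EEGs of preterm infants can quantify sleep duration trends". Section 2.2a adds that "EEG trends over time reveal brain maturation in preterm infants". Section 9.5, Measure 1, describes normal development as "sleep durations gradually increasing by about 5% increments every two weeks until term age".

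The analysis in 9.5 takes "one EEG session for each of the 4 age timepoints, 30 weeks, 32 weeks, 34 weeks, 36 weeks", averages sleep within each session, and then states: "At each timepoint, average sleep duration will be compared between MBI infants and controls". The rule is "Milestone threshold will be reached if >5% longer average durations of sleep are found in the MBI cohort compared to controls in any 1"; a single qualifying recording is therefore enough. The result is given a developmental meaning: "Average sleep duration measurements will determine if MBI promotes/enhances brain maturation".

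The documents contain no slope, change from baseline, baseline adjustment, repeated-measures model or arm-by-age term for sleep. The Tool Revision History (version 2.0b) says the any-visit rule was chosen on purpose, to look for periods of prematurity in which music may have more effect.

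**The concern.** The trend that Objective 2 and the rationale refer to has no analysis. The analysis that is specified sees only the level at each visit, and the first of those visits is the baseline EEG. A gap at 30 weeks cannot show that one arm has matured faster, because no six-week course has yet been observed. The rule still counts that gap, and counts it again at each later EEG to which it persists.

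Two sources of such a gap are plausible from the documents. One is chance imbalance between small arms, since differences between infants tend to persist. The other is an immediate effect of music on sleep: section 2.2 cites one, and the Figure 4 caption in section 3 says the recordings cover an intervention session.

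The milestone feeds the Go/NoGo decision for the R33 phase, so a gap that is not maturation could be carried forward as evidence for Hypothesis 2.

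**Working it through.** **Inputs.** From 9.5: control growth of about 5% per two weeks, EEGs at 30, 32, 34 and 36 weeks, and a threshold of more than 5% at any one. From 9.2: 25 infants per arm with complete data. The documents give no standard deviation or visit-to-visit correlation for sleep. I assume a between-infant coefficient of variation (CV) of 10 to 30% and a correlation of 0.3 to 0.7.

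**The plan's own figure.** Measure 1 has no power figure. The only one is for PIPP in 9.2 (25 per arm, SD 3.6, two-sided 0.05). A t-based calculation gives detectable differences of 2.91 at 80% and 3.11 at 85% power, matching the stated 2.9 and 3.1. It does not bear on this point.

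**1. True means.** The percentage gap at visit k (0 to 3) is (1 + starting gap) × [(1 + music-arm growth)/1.05]^k − 1. The linear six-week change in the gap, with visits at t = 0, 2, 4 and 6 weeks, is 6 × Σ(t − 3) × gap / 20, because 9 + 1 + 1 + 9 = 20.

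| Case | 30 wk | 32 wk | 34 wk | 36 wk | Milestone | Six-week change in gap |
|---|---|---|---|---|---|---|
| Start +6%, same growth (5%) | +6.0 | +6.0 | +6.0 | +6.0 | met | 0.3 × (−18 − 6 + 6 + 18) = 0 |
| Start +6%, slower growth (2.5%) | +6.0 | +3.5 | +1.0 | −1.4 | met | 0.3 × (−18 − 3.5 + 1.0 − 4.2) = −7.4 points |

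In the first row the arms mature at the same rate. In the second the music arm matures more slowly. Both meet the milestone.

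**2. Chance gap at 30 weeks.** With no arm difference, the standard error of the percentage gap is about CV × √(2/25) = 0.283 × CV.
- CV 10%: SE 2.83%. A gap above 5% is 5/2.83 = 1.77 SE, with probability about 4%.
- CV 30%: SE 8.49%. The gap is 5/8.49 = 0.59 SE, with probability about 28%.

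Simulation gave the same 4 to 28%.

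**3. Sampling error with a constant 6% gap.** Simulating 25 per arm over the assumed ranges, under equal correlation or correlation that decays with time, the current rule is met in about 77 to 96% of trials. A criterion of more than 5% difference in linear six-week rise is met in about 2 to 36%.

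**4. Precision of the rise contrast.** Under equal correlation r between visits, the SE of the arm difference in six-week rise, relative to a single-visit comparison, is 6 × √[(1 − r)/20]. This is 1.12 at r = 0.3, 0.95 at 0.5 and 0.73 at 0.7, and it equals 1 at r = 0.44. Under AR(1) with adjacent-visit correlation r, the ratios are 1.39, 1.33 and 1.16 at the same values, with break-even at about 0.80.

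**The case against.** The best defence has four parts.

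- **The plan names duration itself as the indicator.** This stands. Section 1.2 does so, and 9.5 says average durations will decide the matter. A reader might infer that the plan defines maturation as a slope, but the text does not say that. It ties the serial EEGs to trends and then leaves the trend without an analysis.
- **Randomization makes the expected baseline gap zero.** This stands as an expectation. A pre-treatment gap is chance imbalance, and an expected gap that appears only later is a difference in change. But 9.5 counts the 30-week EEG and does not adjust for it, and with 25 per arm the realised gap need not be near zero.
- **The any-visit rule is deliberate.** This stands, and it limits the remedy. A linear term cannot see a transient effect: gaps of 0, +8, +8 and 0% give 0.3 × (0 − 8 + 8 + 0) = 0. A search for critical periods is a reason to keep the visit-specific comparisons. It does not supply the missing trend.
- **The phase is exploratory.** PIPP at 4 weeks is the primary outcome, and the sponsor concedes limited power. This lowers the stakes, but sleep remains one of the Go/NoGo measures.

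A reader might also infer that Measure 1 misses faster maturation for want of a trend analysis. The figures do not support that. From equal baselines, a 30% faster rise gives 19.5% against 15% over six weeks. That is a 4.5-point difference (3.9% of the control level at 36 weeks, or 4.3% with compounding). It falls below 5% at every visit, and the 4.5-point difference in rise is below 5% as well. The miss comes from the threshold.

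**Conclusion.** The point holds in a limited form. Measure 1 does not link an infant's EEGs or estimate change with age, and it lets a gap present at the first EEG count as enhanced maturation. That a constant 6% gap passes at every visit follows from the plan's own figures. The simulated rates (77 to 96% under the current rule, 2 to 36% on the rise) and the 4 to 28% chance of a false pass at 30 weeks rest on the assumed CV, on the assumed correlation for the first two ranges, and on 25 infants per arm at each EEG.

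The documents do not support making the linear rise the sole milestone. The contrast is noisier than a single-visit comparison at low correlation and is blind to a mid-course effect. It also has a limit of its own: if music affects sleep immediately and is heard during later EEGs but not the first, that effect would look like a rise.

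**What to change.** In 9.5, Measure 1:

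1. Fit one mixed model to all per-infant sleep averages from Visits 1 to 4, with arm, age at EEG, arm-by-age, sex (the stratification factor) and a stated within-infant correlation structure. Because the threshold is a percentage, the log scale is natural: a constant percentage gap then contributes nothing to the arm-by-age term.
2. Report the arm difference in six-week rise with its confidence interval, beside the visit-specific differences.
3. Keep the visit-specific comparisons for the critical-period question, but read a difference above 5% as enhanced maturation only if it is not already present at the 30-week EEG.

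This needs SAP wording and one model on EEGs already scheduled, with no new visits or infants. It also uses infants with incomplete EEGs without imputation, consistent with 9.6. The price is a little more analysis and a rise contrast that may be imprecise: noisier than a single-visit comparison when the correlation is below about 0.44 (equal correlation), or about 0.80 between adjacent visits (AR(1)). It should therefore supplement the visit-specific results and not replace them.
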